Recruitment of CAB: Sampling will be purposive. The CAB will consist of 5 older adults who have finished cancer treatment with chemotherapy within the past 3 years, 3 family caregivers, and 2 oncology staff nurses who deliver chemotherapy treatments. Older adults and caregivers are the critical voice of the target audience, and oncology trained nurses are important to verify accuracy of recommended CINV self-management strategies within the game and current treatment center discharge instructions. To the greatest extent possible, all CAB members will be present at each focus group. CAB members will provide input for scenarios (incidence, self-management, perceived and actual consequences) based on their experiences with CINV. Older adults will be recruited from a pool of approximately 109 participants from the PIs prior research studies who agreed to be contacted for further research.

Names will be randomly drawn from this pool; an invitation to participate will be mailed in batches of 10

Figure 3: Principles of Serious Gaming

- Knowledge sets stage for behavioral change
- Practicing skills leads to self-mastery
- Modeling is an effective way to learn new skills
- Tailored games facilitate character identification
- Game must be entertaining

until target numbers are reached. Nurses will be recruited from the UF Health Cancer Center-Orlando chemotherapy treatment center. Retention will be enhanced by offering a \$50 stipend/gift card to the CAB members for each focus group they participate in. Informed consent and participant characteristics (e.g., age, gender, race, educational level, CINV experience) information will be collected from all CAB members.

Phase II - Game prototype testing

Phase II will use a prospective 2-group randomized, longitudinal design to evaluate effect size of the intervention, examine group differences and evaluate game appeal. Patients who meet the inclusion criteria will be randomly assigned into the intervention group or control group at a 1:1 ratio. All participants will be followed for four chemotherapy cycles (approximately 4 months).

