Setting: The outpatient treatment center at the UF Health Cancer Center-Orlando will be the primary site for enrollment due to its long-standing relationship with these researchers. In 2013, UF Health Cancer Center-Orlando saw approximately 4,694 patients. Of these 2,573 patients were age 65 or older, and 565 of these patients received outpatient chemotherapy. These numbers indicate an ample sampling pool of older adults.

Sample size: The target sample is older adults receiving emetogenic chemotherapy for the first time. Sixty-six participants will be enrolled if they meet the following **inclusion criteria**: age 65 and older, newly diagnosed with any cancer, treatment with any chemotherapeutic agent with a moderate to severe emetic potential (on a 3- or 4- week cycle), proficient in English, and have a telephone. **Exclusion criteria** include: previous diagnosis and treatment for cancer, advanced or end stage disease with a palliative intent, visually or hearing impaired. Dementia or cognitive impairment is not a concern with the population since they have already been cognitively screened in order to consent to treatment at this cancer center. There will be no exclusion based on gender or racial/ethnic status. Retention of all participants will be enhanced by the following strategies 1) weekly telephone follow-up phone calls by the RA; 2) a \$50 incentive/gift card at the end of the study period; and 3) attention control group offered eSSET-CINV at the end of the study. We will oversample by 20% in order to account for attrition.

Phase II Procedures:

Recruitment and randomization: Successful recruitment and retention strategies previously established by the team will be used during this phase.^{7, 15, 16, 18, 90} Convenience sampling, followed by randomization will be used. All new patients will be screened for eligibility by the Research Nurse (RN-PG) using the Sunrise XA -

electronic medical record system used by Orlando Health. Eligible patients will be approached by the RN at their first chemotherapy appointment and asked to participate. This timing is not expected to add to or create patient anxiety. Patients usually wait 30 to 60 minutes for lab results and chemotherapy to be delivered. Participating

Table 1: Intervention schema

	Pre-treatment		First Treatment Visit			Post - treatment

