Participant characteristics: Demographic and experiential characteristics that may influence CINV and ability to self-manage this symptom will be measured at T1 (baseline). Demographics include: age, gender, comorbidity information, education level, and income level. Experiential characteristics include: cancer diagnosis and stage, chemotherapy regimen with antiemetics, discharge antiemetic prescriptions, use of the Internet to research symptom management information, and caregiver presence (yes/no) and involvement at home. All cancer information will be collected from the patient's electronic medical record by the RN. Delays in chemotherapy treatment and rationale for delay will also be recorded at each time point by the RN.

Dependent Variables

An overview of study variables, measures and data collection timeline are presented in Table 3. Data will be collected for 4 treatment cycles (3 or 4 months depending on cycle length). Questionnaires will use a paper/pencil format with enlarged font and be entered into Excel™ software.

1) Symptom severity: The *Symptom Representation Questionnaire (SRQ)*⁹¹, a 24-item self-report measure will be used to identify presence and severity of common treatment-related symptoms (0-10 Likert scale), including nausea and vomiting (N/V). This measure asks respondents to think about their symptoms over the past week.

Table 2: eSSET-CINV Intervention process

1	Game introduction and orientation
2	Choose avatar
3	Avatar discharged home after treatment
4	Avatar begins to experience nausea
5	Player makes self-management decisions
6	Avatar responds based on player decisions
7	Avatar experience continues with periodic nausea as player continues to make self-management decisions
8	Game ends when avatar achieves goal of mild or no nausea or has an unplanned ED or hospital admission
9	Discussion of decision choices with Research Nurse

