2) Cognitive representation: The *Symptom Representation Questionnaire (SRQ)*⁹¹ has an additional 15 questions to assess cognitive representation (identity, cause, timeline, consequences, and cure/control) or beliefs about specific symptoms (0-4 agreement scale). This measure includes subscales for symptom cause (2 questions), timeline (3 questions), cure/control (3 questions), and consequence (6 questions). Only the cognitive representation of nausea will be evaluated. This tool is reliable with alpha co-efficients from 0.63 to 0.88 for the subscales.⁹¹ The cognitive representation questions will be modified at baseline to assess participants' beliefs about potential CINV consequences and their ability to be controlled/cured. Subsequent data collection time points will focus on current cognitive representations.

3) Self-management behaviors: An investigator-developed *Symptom Management Checklist [SMC]* will measure CINV: 1) self-management behaviors and 2) prevention behaviors. Participants will complete this daily at home between chemotherapy cycles. When experiencing CINV, the participant will use the SMC to record: 1) CINV severity (0-10 Likert scale) prior to self-management, 2) the *type* of self-management strategies used and, 3) the strategies *perceived helpfulness* in reducing nausea (0-10 Likert scale). Preventative self-management activities for CINV will also be recorded. All self-management strategies are coded (e.g., “MED”= taking antiemetic, “DIS”- using distraction), and the participants will fill in the strategy code they are using on the form. To lessen the risk of the SMC becoming an intervention for the Control Group, all participants will be asked to record self-management behaviors of other common treatment-related symptoms (i.e. fatigue, mouth/throat sores). The SMC will be collected by the research nurse at chemotherapy cycles 2, 3 and 4.

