Willingness to recommend the game will be assessed using one item: Would you recommend this game to other older adults about to start chemotherapy treatment (yes/no)? This will be collected at Cycle 4 (T4).

Table 3: Summary of dependent variables, measures and data collection time points

		Data Collection Time points			
Dependent Variable/Outcome s	Measure	T1 Baseline	T2 Cycle 2	T3 Cycle 3	T4 Cycle 4
Symptom severity	SRQ- patient report	x	x	x	x
Cognitive representation	SRQ-patient report	x	x	x	x
Self-management behaviors*	SMC- patient report		x	x	x
Resource Use	Patient report		x	x	x
QOL	EORTC-patient report	x	x	x	x

*Note: self-management behaviors will be recorded daily by participants, but collected by the research nurse at each treatment visit

DATA ANALYSIS

Phase I: Game prototype and production

AIM 1: Identify real-life scenarios involving CINV incidence, self-management, and consequences using a peer Community Advisory Board of older adults who have undergone cancer treatment, their family members, and oncology nurses to design and develop a serious game for CINV self-care decision making.

AIM 2: Identify design aspects and elements of eSSET-CINV game play, audio, and visual avatar development that have the greatest appeal for older adults with cancer.

Data from focus groups will be digitally audio-recorded and transcribed. Methods consistent with classic content analysis will be used to analyze data from the focus groups and will begin immediately after each focus group.⁹⁴ The focus group recordings will be reviewed by the PI and student RAs and content analysis will be conducted to thematically categorize responses. Data will be de-identified in analysis-no names will be used. In order to eliminate bias, the analysis will remain grounded in the data. Themes will be created and coded using language similar to what the participants use. These codes will then be grouped by similarity and used to summarize feedback about the game and suggestions for improvement.⁹⁴ The notes taken by the RAs during and after the focus groups will serve as a “trail of evidence” to increase the trustworthiness of the data and confirm final findings. Data are not intended to be generalized but will answer specific study AIMS.

Phase II: Game prototype testing

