Preliminary data analysis: Descriptive statistics will be provided to characterize the study participants for all demographic and experiential variables at baseline and at each treatment cycle time point. Summary tables will be provided to present participant characteristics (e.g., gender, age group, race), major study variables, game appeal, and willingness to recommend game to others. Internal consistency of study measures will be checked and evaluated to ensure data quality. Effort will be taken as much as possible to avoid missing data. If there are significant missing data that may impact analysis results, the multiple imputation method may be used for the analysis of primary endpoint. All statistical analyses will be performed using Statistical Application Packages (SAS®), version 9.4.

Principle data analysis: The primary endpoints for the study are N/V severity score and the number of self-management behaviors. The secondary endpoints are ED/hospital admission and QOL. Summary statistics for the primary and secondary endpoints will be provided. The t-test will be used if the normality of the endpoint can be confirmed. Otherwise, the Wilcoxon Rank-Sum test will be used to assess the difference between the two groups at each treatment cycle time point.

AIM 1: Estimate effect size of the eSSET-CINV in changing patient outcomes: cognitive representation, self-management behaviors, CINV severity, QOL, and resource use. The effect size of N/V severity score will be estimated using the Cohen’s d, which is defined as the difference between two means divided by a standard deviation for the data.

AIM 2: Examine differences in cognitive representation, self-management behaviors, CINV severity, QOL, and resource use, between, and within, the intervention and attention control groups. For the primary endpoints, the data will be collected over 4 treatment cycles, and the method of analysis of longitudinal data will be used to compare the difference between intervention and control groups over time. The generalized estimating equation (GEE) approach may be used to enhance the robustness of the estimation of model parameters when the ideal working correlation structure is difficult to pre-specify. In the longitudinal model treatment cycle time, interaction of time and treatment, or both, whenever feasible, may be added into the model to assess the time effect on treatment difference.

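### Both primary endpoints have three post-treatment assessments, looking back on cycles 1 to 3, although the plan says their data span four treatment cycles

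*Combined protocol and SAP*

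**What the plan says.** Three statements give the period as four cycles. The opening paragraph of Phase II - Game prototype testing says "All participants will be followed for four chemotherapy cycles (approximately 4 months". The opening of Dependent Variables says "Data will be collected for 4 treatment cycles (3 or 4 months depending on cycle length". The Aim 2 paragraph of Data Analysis says "For the primary endpoints, the data will be collected over 4 treatment cycles". Under Principle data analysis, "The primary endpoints for the study are N/V severity score and the number of self-management behaviors".

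The schedule is set out elsewhere:

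- **Enrolment and T1.** Under Recruitment and randomization, "Eligible patients will be approached by the RN at their first chemotherapy appointment and asked to participate". Baseline measures follow consent and precede randomisation. The intervention arm plays the game before the first infusion.
- **T2 to T4.** Table 3 labels its four columns as baseline, cycle 2, cycle 3 and cycle 4, and has no later column. Of the game recommendation item the plan says "This will be collected at Cycle 4 (T4".
- **Self-management.** The SMC is filled in daily at home in the gaps between cycles, and "The SMC will be collected by the research nurse at chemotherapy cycles 2, 3 and 4". Table 3 has no SMC entry at T1, and its footnote ties collection to treatment visits.
- **Severity.** The SRQ is scheduled at T1 to T4 and asks about the preceding week.
- **Cycle length.** The inclusion criteria require chemotherapy "on a 3- or 4- week cycle".

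**The concern.** The text counts four cycles of primary-endpoint data. The schedule has four visits, of which the first is before treatment and the last opens cycle 4. Four visits enclose three cycles.

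Two things are at stake. The first is description: a report of effects over four cycles would claim a cycle in which neither primary endpoint was measured. The second is the analysis. Aim 2 calls for a longitudinal comparison over the four cycles, and group comparisons at each cycle time point for every primary and secondary endpoint. It makes the time and time-by-treatment terms optional. An analyst who takes four cycles to mean four outcome points would look for an SMC value at T1 that does not exist. For severity, the same analyst would include a measurement taken before randomisation, where the expected group difference is zero. The first Phase II aim is to estimate effect size, so an averaged estimate that includes such a point would bear directly on the trial's purpose.

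**Working it through.** **Inputs.** Cycle length is 3 or 4 weeks (inclusion criteria). Four cycles are stated (Phase II opening, Dependent Variables, Aim 2). The visits are T1 before dose 1 and T2, T3 and T4 at cycles 2, 3 and 4 (Recruitment and randomization; Table 3). SRQ recall is one week (Symptom severity). The planning difference is 1 point and the standard deviation 2.44 (Sample size and statistical power).

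**1. The plan's own figure.** Four full cycles = 4 × cycle length.
- 3-week cycles: 4 × 3 = 12 weeks; at 4.35 weeks per month, 2.8 months.
- 4-week cycles: 4 × 4 = 16 weeks, or 3.7 months.

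This reproduces the 3 or 4 months under Dependent Variables, so that statement counts four complete cycles. The flat 4 months in the Phase II opening fits only 4-week cycles.

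**2. The scheduled span.** Intervals from T1 to T4 = 4 visits − 1 = 3.
- 3-week cycles: 3 × 3 = 9 weeks, or 2.1 months.
- 4-week cycles: 3 × 4 = 12 weeks, or 2.8 months.

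The shortfall is one cycle in four (25%), assuming no treatment delays.

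**3. What each primary endpoint covers.**

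| Endpoint | Pre-treatment value | Post-treatment collections | Time covered after dose 1 |
|---|---|---|---|
| Number of self-management behaviors (daily SMC) | none | 3 (T2, T3, T4) | cycles 1 to 3: 9 or 12 weeks |
| N/V severity (SRQ) | T1 | 3 (T2, T3, T4) | last week of each of cycles 1 to 3: 3 weeks in all |

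**4. Could T4 mean the end of cycle 4?** The SMC is collected at treatment visits and records the gaps between cycles. If the T4 collection closed cycle 4, T2 would close cycle 2, and cycle 1 would have no collection of its own. The SMC has three collections on any reading.

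**5. Effect of counting T1 as an outcome.** Suppose the true group difference is 0 at T1 and a constant Δ at T2, T3 and T4. With equal weights and no time-by-treatment term, the averaged difference is (0 + Δ + Δ + Δ)/4 = 0.75Δ. For the planning difference Δ = 1 this gives 0.75 points. As a standardised effect, 1/2.44 = 0.41 becomes 0.75/2.44 = 0.31.

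**The case against.** The best defence is that Table 3 already discloses the schedule. It labels T1 as baseline, leaves the SMC blank there and names the other visits by cycle, so the fault is loose prose beside a clear table. The plan also leaves the window that defines a cycle to be settled later, and nowhere states a model with four outcome points. All of this stands. It limits the point to coverage wording and an unspecified role for T1. The dilution is a risk that the optional terms leave open; it is not an analysis the plan prescribes.

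Some stronger readings are tempting but are not supported:

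- **That nothing at all is collected after the cycle 4 dose.** The weekly calls have no stated end date, and the Resource Use paragraph records ED and hospital admissions at each phone contact. Following participants through cycle 4 may be intended, and the schedule does not contradict it. The calls are not described as collecting the SRQ or SMC.
- **That both primary endpoints cover 9 or 12 weeks.** This is true of the daily SMC only, because the SRQ looks back one week.
- **That the missing cycle costs a known amount of precision or power.** The plan gives no within-patient correlation and defines no visit-averaged outcome. Its sample size rests on a single mean difference and standard deviation, with no number of visits.

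A baseline covariate is not the only valid choice. A longitudinal model that keeps T1 as a response is sound if the time-by-treatment term is always included.

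**Conclusion.** The point holds for the two primary endpoints. Each has three post-treatment assessments (T2 to T4), which look back on cycles 1 to 3. Neither has data after the cycle 4 dose, although Dependent Variables and Aim 2 claim four cycles. The T1 to T4 span is 9 or 12 weeks against 12 or 16, provided there are no delays; the plan expects to record delays, so actual spans may be longer.

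The consequence is moderate. A reader might infer that the randomised comparison is compromised, but both arms follow the same collection schedule, and comparisons at T2, T3 or T4 are unaffected. The analytic risk is confined to a severity estimate that pools T1 with the later visits. Its size, three quarters of the true effect, assumes a constant effect after treatment, equal weighting of the visits and no interaction term. The correction should be made before analysis, because it costs little and settles both what is estimated and what may be reported.

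**What to change.** 1. **Coverage wording.** In Dependent Variables and Aim 2, state that the primary endpoints have three post-treatment assessments, T2 to T4, relating to cycles 1 to 3. Say that the SMC covers the full intervals and that SRQ severity reflects the last week of each. Reconcile the Phase II opening paragraph with this, including its flat 4 months, and state when the weekly calls and the recording of resource use end. Cost: wording only.
2. **Analysis.** For N/V severity, name T2 to T4 as outcomes and T1 severity as a covariate. Alternatively, keep T1 as a response with a mandatory time-by-treatment term and take the effect from T2 to T4. For self-management, state that there are three time points and no baseline. Cost: a few sentences in the analysis section, using data already scheduled.
3. **Optional.** If the sponsor wishes to keep the four-cycle statement, add one SRQ and SMC return at the end of cycle 4. Cost: one further set of forms per participant, for example by mail, with reminder calls continuing through that cycle.

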The one-way repeated measures ANOVA will be used to assess the difference between the two groups. The mixed effect model may be used as exploratory analysis to account for unobservable variations from each individual patient. In addition, comparisons between two groups at each treatment cycle time point will be performed for all primary and secondary endpoints. For this particular comparison, the univariate normality of each endpoint will be assessed graphically at each treatment cycle time point. An appropriate time window will be determined to define the treatment cycles for the study.

AIM 3: Obtain preliminary data regarding the feasibility and acceptability of the game in older adults experiencing CINV. Feasibility- Computer science and digital media undergraduate students will work under the direction of [name] and [name] to identify patterns in game play data (e.g., self-management decisions, scenario patterns of progression), time to game completion, and number of times the game was played (intervention dose). The RN will track any instance of game play interruptions or

malfuction. This data will be summarized with descriptive statistics. **Game Appeal:** Responses to the game appeal and willingness to recommend questions will be scored and summed using descriptive statistics. Additional comments about the game will be recorded and analyzed for themes.

Sample size and statistical power:

Based on the assumption of a nausea severity mean score of 6.20, range from 2 to 9, a standard deviation of 2.44, and a clinically meaningful difference in mean nausea severity score of one between the intervention and control groups, with 90% power, the required sample size is 33 participants for each group, yielding a total sample size of 66 for the study. To reduce the patient selection bias, single-blinded randomization may be used whenever feasible. Due to lack of available data from prior research the sample size for secondary endpoints is not possible for the study at first stage. However, the power statistical analysis will be assessed when data become available from the planned study.

Potential challenges and strategies for addressing:

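### The promised 20% oversample is not in the enrolment figure: 66 is both the number to enrol and the number required

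*Combined protocol and SAP*

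**What the plan says.** Three statements bear on this point.

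- Phase II, Sample size paragraph (under Setting), on enrolment: "Sixty-six participants will be enrolled if they meet the following" inclusion criteria.
- The last sentence of the same paragraph: "We will oversample by 20% in order to account for attrition".
- Data Analysis, Sample size and statistical power: "the required sample size is 33 participants for each group, yielding a total sample size of 66 for the study". This rests on "a clinically meaningful difference in mean nausea severity score of one between the intervention and control groups", "a standard deviation of 2.44" and 90% power. It has no term for attrition.

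Allocation is 1:1, and follow-up runs over four chemotherapy cycles, about four months. The documents give no enrolment total that includes the 20%, no expected loss rate, and no significance level.

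**The concern.** The same number does two jobs. As the required sample, 66 is what the power statement needs for analysis. As the enrolment figure, 66 is counted at the first treatment visit, where Table 1 places enrolment and randomisation, before anyone can be lost. If 66 are enrolled, nothing has been oversampled. If 20% is added, the enrolment number is not 66.

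Staff who take the enrolment sentence at its word would stop at 66 and end below the required number after any loss. Readers of the protocol, meanwhile, are told that attrition has been allowed for. Loss is a realistic prospect in patients aged 65 and older over about four months of emetogenic chemotherapy, and the plan itself anticipates it.

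**Working it through.** **Inputs.** From the plan: 66 enrolled; 66 required (33 per group); 20% oversample; difference 1 point; SD 2.44; 90% power; 1:1 allocation; two-group t-test at each time point (Principle data analysis). Assumed, because not stated: two-sided alpha 0.05, and a loss of 16.7% to 20%.

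**1. The plan's own figure.** Normal approximation: n per group = 2 × [SD × (1.960 + 1.282) / difference]² = 2 × (2.44 × 3.242)² ≈ 125.1, so 126. The exact t calculation gives 126.1. The stated 33 does not reproduce. One-sided 0.05 gives 102 per group, and one-sided 0.10 gives 79. This error is separate from attrition. It matters here only because 33 can be used as the plan's stated requirement but not as a number that delivers 90% power.

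**2. What a 20% oversample covers.** 66 × 1.20 = 79.2, so 80 with equal arms (40 per group). The loss that a factor of 1.2 offsets is 1 − 1/1.2 = 16.7%. A 20% loss needs division instead: 66 / 0.8 = 82.5, so 83, or 84 with equal arms.

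**3. What remains under each reading.**

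| Enrolled | Loss | Remaining | Per group |
|---|---|---|---|
| 66 | 16.7% | 66 / 1.2 = 55 | 27 or 28 |
| 66 | 20% | 66 × 0.8 = 52.8 | about 26 |
| 80 | 20% | 80 × 0.8 = 64 | 32 |
| 84 | 20% | 84 × 0.8 = 67.2 | about 33 |

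**4. Effect on power at one time point.** Standardised difference = 1 / 2.44 = 0.41. Two-sample t-test, two-sided 0.05:

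- 33 per group: 37.5%
- 27 per group: 31.5%
- 26 per group: 30.5%

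**5. Effect on precision.** The standard error of the difference is 2.44 × √(2/n). It is 0.60 points at n = 33 and 0.68 at n = 26. The ratio is √(33/26) = 1.13, so confidence intervals are about 13% wider.

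**The case against.** The strongest reply is that the sentences can be reconciled. Nothing calls 66 a cap, and the oversampling sentence states an intention to go beyond the base number. Read that way, 66 is the evaluable target, about 80 are recruited, and a 20% loss leaves 64, or 32 per group, close to the planned 33. This stands as a possible reading, and it makes the shortfall conditional. It does not remove the defect. The only enrolment number given is 66, its verb is enrolment, and the reader must supply 80 unaided.

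Two stronger conclusions are tempting, and the documents support neither.

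- A reader might infer that the trial will end with 26 per group because it expects to lose 20%. The plan states an oversampling rate, not an expected loss. The figure of 26 needs both a stop at 66 and an assumed 20% loss.
- A reader might infer a fall in power from 90% to about 82%. That holds only if 33 per group gave 90%, which needs a difference of about 1.95 points. The plan states one point.

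It is also fair to say that the completer calculation is pessimistic for the longitudinal comparison. Severity is measured at four time points, and the analysis under Aim 2 uses repeated measures, with GEE and mixed models as options. Someone lost after cycle 2 or 3 can still contribute. The power figures above therefore describe a single time point and may overstate the cost for the longitudinal analysis. Multiple imputation is mentioned only as something that may be used, so it is not a committed safeguard. Finally, Phase II aims first to estimate an effect size, and for that purpose the 13% loss of precision is the more relevant measure.

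**Conclusion.** The point holds as an inconsistency in the stated numbers. The enrolment figure equals the required figure, the promised 20% is in neither, and no inflated total is given.

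Its size depends on how the plan is carried out. If enrolment stops at 66, between about 53 (at 20% loss) and 55 (at 16.7% loss) remain. On the stated 1-point difference and SD 2.44, with two-sided 0.05 assumed, 26 rather than 33 completers per group takes single-time-point power from 37.5% to 30.5%. If about 80 are enrolled, the shortfall largely disappears: none up to about 17% loss, and 64 remaining at 20%. In neither case does settling attrition restore the stated 90% power, since the plan's inputs need about 126 per group.

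**What to change.** State whether 66 is the enrolled or the evaluable number, and carry one figure through both sections. There are two ways to do this.

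- **Evaluable 66.** Replace 66 in the enrolment sentence with 80 (66 × 1.2), and say that this covers a loss of up to about 17%. If a 20% loss is to be covered, the number is 83, or 84 with equal arms. This means 14 more participants than 66 (17 or 18 more for a 20% loss), but 80 only carries out the oversample already promised. The site reports 565 patients aged 65 or older on outpatient chemotherapy in 2013, though not all would be eligible.
- **Enrolled 66.** Keep the enrolment sentence, delete the oversampling sentence, and restate the expected number with outcome data as about 53 to 55, with the power or precision it gives. This needs no extra patients. Its cost is a less favourable statement and the loss of the attrition allowance.

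Either way, name the assumed loss rate. The change is to protocol wording. The power inputs need their own correction, and if that changes the required number, the attrition allowance should be reapplied to the new figure.
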